### 11.1 Correlative collection calendar

Time Point	Correlative	Bone Marrow collection	Peripheral Blood Collection
Baseline			
Correlatives: Flow cytometry, Cytogenetics, Next-generation sequencing, Tetramer Analysis, and DNA methylation		X	X
Day 28 +/- 1 day of cycles 1, 2, and 3			
Correlatives: Flow cytometry, Cytogenetics, Next-generation sequencing, Tetramer Analysis, and DNA methylation		X	X
Day 28 +/- 1 day every 3 cycles starting with cycle 6 (ex. Cycles 6, 9, 12...)			
Correlatives: Flow cytometry, Cytogenetics, Next-generation sequencing, Tetramer Analysis, and DNA methylation		X	X
Day 28 +/- 1 day of end of every cycle starting with cycle 4 (excluding cycles 6, 9, 12... as above)			
Correlatives: DNA methylation			X
End of Treatment/Relapse			
Correlatives: Flow cytometry, Cytogenetics, Next-generation sequencing, Tetramer Analysis, and DNA methylation		X	X

## 12. MEASUREMENT OF EFFECT

Although the clinical benefit of this drug combination has not yet been established, the intent of offering this treatment is to provide a possible therapeutic benefit, and thus the patient will be carefully monitored for tumor response and symptom relief in addition to safety and tolerability. Patients with measurable disease will be assessed by standard criteria. For the purposes of this study, patients should be re-evaluated with bone marrow biopsies as per the study calendar.

### 12.1 Antitumor Effect – Hematologic Tumors

Assessment of clinical response will be made according to the International Working Group criteria {Cheson 2003}. The major criteria for judging response will include physical examination and examination of blood and bone marrow. All laboratory studies that are abnormal prior to study will be repeated to document the degree of maximal response.

#### Morphologic Leukemia-free State (MLFS)

MLFS requires all of the following:

- 12.1.1 < 5% blasts in bone marrow aspirate
- 12.1.2 No extramedullary disease
- 12.1.3 No blasts with Auer rods

#### detected Morphologic Complete Remission (CR) CR requires all of the following:< 5% blasts in bone marrow aspirate

- 12.1.4 < 5% blasts in bone marrow aspirate
- 12.1.5 Neutrophils  $\geq 1,000/\mu\text{L}$
- 12.1.6 Platelets  $\geq 100,000/\mu\text{L}$
- 12.1.7 No extramedullary disease
- 12.1.8 No blasts with Auer rods detected
- 12.1.9 Independent of transfusions

#### Cytogenetic Complete Remission (CRc)

CRc requires all of the following:

- 12.1.10 < 5% blasts in bone marrow aspirate
- 12.1.11 Neutrophils  $\geq 1,000/\mu\text{L}$
- 12.1.12 Platelets  $\geq 100,000/\mu\text{L}$
- 12.1.13 No extramedullary disease
- 12.1.14 No blasts with Auer rods detected
- 12.1.15 Independent of transfusions
- 12.1.16 Reversion to a normal karyotype with an abnormal karyotype at the time of diagnosis

### **Morphologic CR with incomplete blood count recovery (CRi)**

CRi requires all of the following:

- 12.1.17** < 5% blasts in bone marrow aspirate
- 12.1.18** Neutrophils < 1,000/ $\mu$ L or Platelets < 100,000/ $\mu$ L
- 12.1.19** No extramedullary disease
- 12.1.20** No blasts with Auer rods detected
- 12.1.21** If blood counts recover within 14 days of a bone marrow evaluation that is consistent with CRi, the patient will be considered CR at the time when both neutrophil and platelet count recover (neutrophils  $\geq$  1,000/ $\mu$ L, platelets  $\geq$  100,000/ $\mu$ L).

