1 out of 3	
Enter 3 more subjects at this dose level.
 
 
• If 0 of these 3 subjects experience DLT, proceed to the next dose level.
 
• If 1 or more of this group suffer DLT, then dose escalation is stopped, and this dose is declared the maximally administered dose. Three (3) additional subjects will be entered at the next lowest dose level if only 3 subjects were treated previously at that dose.
 

$\geq 2$	Dose escalation will be stopped. This dose level will be declared the maximally administered dose (highest dose administered). Three (3) additional subjects will be entered at the next lowest dose level if only 3 subjects were treated previously at that dose.
$\leq 1$ out of 6 at highest dose level below the maximally administered dose	This is generally the recommended maximally tolerated dose. At least 6 subjects should be entered at the recommended phase 2 dose.

We expect to enroll a minimum of 6 patients (6 patients treated at DL 1 with 1 or less patient experience DLT) and a maximum of 18 patients (6 at each of the DL 1, -1 and -2) for dose finding part. Once the MTD is determined, patients will be accrued to the expansion cohort to be treated at MTD. Including 6 patients treated at MTD from the dose escalation part, we plan to accrual additional 24 R/R AML patients to the expansion cohort. A total of 30 patients will be treated at MTD to decide whether the response rate (CR rate), P, is less than or equal to 30% (combination drug not of interest) or greater than or equal to 50% (combination drug is promising). If the number of responses out of 30 patients is 13 or more, the hypothesis that  $P \leq 30\%$  is rejected with a target error rate of 0.10 and an actual error rate of 0.084. If the number of

responses is 12 or less, the hypothesis that  $P \geq 50\%$  is rejected with a target error rate of 0.20 and an actual error rate of 0.181.

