To estimate the response rate, defined by CR/Cri, which will be assessed by bone marrow biopsy after cycle 1, cycle 2, cycle 3, then every 3 cycles after this, and at time of relapse. Since this will study will only have a small sample size, it will not be powered to determine an accurate response rate for nivolumab in combination with venetoclax and decitabine. We will plan to estimate response rate, as defined by CR/CRI in all evaluable patients in this study, regardless of dose level of venetoclax, and will not attempt to evaluate response rate for individual dose levels. The response rate along with an exact 95% confidence interval will be reported. However, we can consider our study's response rate in context of recent retrospective studies evaluating venetoclax in combination with HMA as well as the historical response rate with high dose cytarabine-containing regimens where the CR rate is 30-40%. Therefore, a response rate of 50% would be considered promising.

Toxicity will be graded and reported according to the revised NCI Common Terminology Criteria for Adverse Events (CTCAE) version 5.0. All patients who receive any amount of the study drug (Nivolumab) will be evaluable for toxicity.

Dosing schema and dosing alterations can be found in [Section 6.1](#) and [Section 7](#).

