### **Complete remission with hematological improvement (CRh)**

CRh meets all Criteria for CR except for residual thrombocytopenia and/or neutropenia defined as:

- Bone marrow blasts < 5%
- Absence of circulating blasts on differential from peripheral blood (as determined by flow cytometry or blasts with morphologic Auer rods)
- Absence of extramedullary disease
- Absolute neutrophil count  $> 500/\mu$ L
- Platelet count  $> 50,000/\mu$ L

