### **Treatment Failure (TF)**

Treatment failure will be classified as one of the following:

- 12.1.27** Resistant disease: Failure to achieve a complete remission (CR, CRc, or CRi) or partial remission. Patients who survive  $\geq 7$  days following completion of initial treatment, with evidence of persistent leukemia by blood and/or bone marrow examination.
- 12.1.28** Death in Aplasia: Patients who survive  $\geq 7$  days following completion of initial treatment, but die while cytopenic, with an aplastic or hypoplastic marrow obtained within 7 days of death, without evidence of persistent leukemia

**12.1.29** Death from Indeterminate cause: Patients who die before completion of treatment or < 7 days following completion of initial treatment; patients who die  $\geq$  7 days following completion of initial treatment with no peripheral blood blasts, but no bone marrow examination is available; patients who fail to complete the first cycle of therapy

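### The 13-of-30 rule is tied to the CR rate while the next paragraph defines response as CR/CRi in a different population; and if *or* in 12.1.18 is inclusive, CRi takes in every low-count MLFS

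*Combined protocol and SAP*

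**What the plan says.** **The efficacy rule (section 9.1).** Thirty patients at the MTD (six from dose finding plus 24 more) are used "to decide whether the response rate (CR rate), P, is less than or equal to 30" percent, or at least 50%. Thirteen or more responses reject the lower value. The stated actual error rates are 0.084 and 0.181.

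**The following paragraph of 9.1.** It says: "We will plan to estimate response rate, as defined by CR/CRI in all evaluable patients in this study". It pools all venetoclax dose levels, promises an exact 95% interval, cites a historical CR rate of 30-40% for cytarabine regimens, and concludes that a 50% response rate would be promising.

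**The secondary objectives.** Objective 1.2.1 is CR+CRi. Objective 1.2.2 is CR+CRi+CRh+MLFS.

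**The category definitions (section 12.1).**
- CRi: under 5% marrow blasts, no extramedullary disease, no Auer rods, and "Neutrophils < 1,000/ $\mu$ L or Platelets < 100,000/ $\mu$ L". No minimum count is given.
- MLFS: "MLFS requires all of the following", and the list is those same three marrow and disease items. It has no count condition and does not exclude CR, CRi or CRh.
- CRh: "CRh meets all Criteria for CR except for residual thrombocytopenia and/or neutropenia defined as" neutrophils above 500 and platelets above 50,000, with blast and extramedullary conditions.
- CR: both counts recovered and transfusion independence.

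Sections 9.1, 9.3 and 12.1 give no ranking and no rule assigning one category per patient.

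**The concern.** There are two separate problems.

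First, the only efficacy decision rule in the plan is attached to one endpoint and one population, while the paragraph that interprets the response rate uses another of each and keeps the 50% yardstick. With both counts in hand at the end of the trial, the text does not settle which one is compared with 13. The historical figure offered in support is a CR rate, yet it is set beside a response defined as CR/CRi.

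Second, 1.2.1 and 1.2.2 are meant to be two rates, a stricter one and a broader one. If CRi has no count floor and takes in any patient with either count low, nearly every MLFS patient already counts in the stricter rate. The composite CR rate would then largely measure marrow clearance, and reporting the two rates separately would tell the reader little.

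**Working it through.** **1. The plan's own figures.** Inputs from 9.1: n = 30, cut-off 13, 30% and 50%. With X binomial,

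P(X ≥ 13 | p) = Σ (k = 13 to 30) C(30,k) p^k (1−p)^(30−k).

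- p = 0.30: 0.0845 (0.08447), matching the printed 0.084.
- p = 0.50: 0.8192, so P(X ≤ 12) = 0.1808, matching the printed 0.181.

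These depend only on n, the cut-off and p, so they are right for CR or for CR/CRi.

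**2. How much the endpoint matters.** Section 2.4.1 cites 13 CR and 10 CRi among 55 relapsed/refractory patients on 10-day decitabine plus venetoclax.

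| Endpoint for the rule | Cited rate | P(X ≥ 13 of 30) |
|---|---|---|
| CR | 13/55 = 23.6% | 0.014 |
| CR/CRi | (13 + 10)/55 = 23/55 = 41.8% | 0.503 |

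This illustrates the endpoint choice only. The rates are for two drugs, under that study's response definitions, which the documents do not give.

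**3. How far the populations differ.** Dose finding takes at most 18 patients, of whom six are at the MTD and join the 24 expansion patients: 6 + 24 = 30. The other 18 − 6 = 12 (42 − 30 = 12) can enter the all-evaluable estimate but not the 13-of-30 count.

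**4. Category overlap.** Take patients who meet the marrow and disease criteria. Cross three neutrophil bands (≤500; between 500 and 1,000; ≥1,000) with three platelet bands (≤50,000; between 50,000 and 100,000; ≥100,000) and transfusion independence (yes or no): 3 × 3 × 2 = 18 combinations. CR is 1 of these. MLFS as written covers all 18. The CRh header is read as keeping the transfusion condition.

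| | *or* inclusive | *or* = exactly one low |
|---|---|---|
| CRi | (9 − 1) × 2 = 16 | (2 + 2) × 2 = 8 |
| CR+CRi (1.2.1) | 16 + 1 = 17 | 8 + 1 = 9 |
| Added by CRh | 0 | 1 |
| Added by MLFS | 1 | 8 |
| Overall response (1.2.2) | 18 | 18 |

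On the inclusive reading, the single combination separating the two objectives is full counts without transfusion independence. These are logical combinations, not shares of patients.

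**The case against.** **The overlap turns on one word and an unseen source.** Section 12.1 opens with "Assessment of clinical response will be made according to the International Working Group criteria", and those criteria are not reproduced. They may rank the categories or separate MLFS from CRi. The CRh text writes *and/or* where 12.1.18 writes only *or*, which leaves room for the one-lineage reading. This stands, and it limits the second problem to the inclusive reading. Support for that reading is mixed. Item 12.1.21 says "the patient will be considered CR at the time when both neutrophil and platelet count recover", but CR needs both counts anyway, so this fits either reading. Section 6.5.1 is better support: it deals with Grade 4 neutropenia and thrombocytopenia together in patients still in CR/CRi. It is a dose-reduction passage, however, not a definition.

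**The symbol P appears once.** It is attached only to the CR rate, so it would be too strong to say that P itself carries two definitions. The second paragraph can be read as a separate estimation exercise, and it says that the study is not powered for an accurate response rate. That is fair, but the paragraph reuses the term response rate and the 50% benchmark without saying that it is separate.

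**Further inferences that the documents do not support.** A reader might add that CRh lies inside CRi. On the inclusive reading that is so, but it changes neither rate. A reader might also infer that one marrow can be scored both as CRi and as Death in Aplasia ("but die while cytopenic, with an aplastic or hypoplastic marrow obtained within 7 days of death"). That needs an assumed meaning of cytopenic, which the protocol does not define, and treatment failure is not an endpoint in section 1 or section 9.

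**Conclusion.** Both parts hold in limited form.

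The endpoint conflict in 9.1 does not depend on how 12.1.18 is read. The rule is for CR in 30 patients at the MTD, and the response rate is CR/CRi in all evaluable patients at any dose level. At the cited two-drug rates the choice of endpoint moves the chance of meeting the rule from 0.014 to 0.503. A reader might take 0.503 as the rule's false-positive rate. It is not: the design's error rate is defined at 30%, and 0.084 is correct there.

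The near-coincidence of 1.2.1 and 1.2.2 holds only if *or* is inclusive. Even then the two rates are not identical, because patients with full counts who are not transfusion independent count only in 1.2.2. How many patients would move between categories cannot be computed from the documents.

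The primary safety/MTD objective is not affected. The ambiguities should still be resolved, because the stated rules either conflict or let the composite CR rate absorb MLFS.

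**What to change.** **Section 9.1.** Name one endpoint, CR or CR/CRi, and one population for the 13-of-30 rule, and justify 30% and 50% for that endpoint. Label the all-evaluable, all-dose-level estimate as a separate descriptive analysis.

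**Sections 9.3 and 12.1.** Assign each patient one best response from ranked, mutually exclusive categories. Define MLFS as the residual: marrow criteria met without CR, CRi or CRh. The sponsor should state whether *or* in 12.1.18 is inclusive and what separates CRi from MLFS.

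**Cost.** The analysis changes are wording, using marrows and counts already collected. The reported CR/CRi rate may be lower. The Schema, section 6.5.1 and the treatment paragraphs of 9.1 use the same labels to direct treatment, and MLFS is not among the labels that lead to maintenance. Changing the CRi wording can therefore change who meets those conditions. The sponsor must reconcile those passages; no clinical rule is proposed here.

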### **Complete remission with hematological improvement (CRh)**

CRh meets all Criteria for CR except for residual thrombocytopenia and/or neutropenia defined as:

- Bone marrow blasts < 5%
- Absence of circulating blasts on differential from peripheral blood (as determined by flow cytometry or blasts with morphologic Auer rods)
- Absence of extramedullary disease
- Absolute neutrophil count  $> 500/\mu$ L
- Platelet count  $> 50,000/\mu$ L

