### **Relapse**

Relapse is defined as:

**12.1.30** Evidence of morphologic relapse with the reappearance of leukemic blasts in the peripheral blood, blasts with Auer rods,  $\geq$  5% blasts in the bone marrow, or evidence of extramedullary disease not attributable to any other cause. In the setting of recent treatment, if there are no circulating blasts and the bone marrow contains 5-20% blasts, a bone marrow biopsy should be repeated within 1 week to distinguish relapse from bone marrow regeneration.

**12.1.31** The reappearance of cytologically proven extramedullary disease also indicates relapse. Reappearance of a cytogenetic abnormality is considered a cytogenetic relapse. Evidence of bone marrow morphologic involvement or extramedullary disease required.

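### The lists for CR, CRc, CRi and MLFS omit absence of circulating blasts, which CRh requires, so a patient with leukaemic blasts in the blood can be counted as a responder

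*Combined protocol and SAP*

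**What the plan says.** All the definitions are in Section 12.1 of the combined protocol and SAP.

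- **MLFS** ("MLFS requires all of the following"): marrow blasts below 5%, no extramedullary disease, no Auer-rod blasts.
- **CR** ("CR requires all of the following"): the same three items, plus neutrophils of at least 1,000/µL, platelets of at least 100,000/µL and transfusion independence. Apart from the marrow percentage, its only blast item is "No blasts with Auer rods detected", with no site named.
- **CRc**: the CR list plus reversion to a normal karyotype.
- **CRi** ("CRi requires all of the following"): the three MLFS items with neutrophils or platelets below the CR threshold.
- **CRh**: introduced with "CRh meets all Criteria for CR except for residual thrombocytopenia and/or neutropenia defined as", followed by a list that includes "Absence of circulating blasts on differential from peripheral blood (as determined by flow cytometry or blasts with morphologic Auer rods".
- **Relapse** (12.1.30): "Evidence of morphologic relapse with the reappearance of leukemic blasts in the peripheral blood" is one of several alternatives. The last sentence of 12.1.31 asks for marrow or extramedullary involvement without saying whether it covers all relapse or only cytogenetic relapse.

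The opening of 12.1 cites the International Working Group criteria and says blood and marrow are examined, but sets no rule for blasts in the blood. No section says which category prevails when a patient meets two.

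**The concern.** CRh is presented as the lesser category: CR without full count recovery. It nevertheless carries a disease-clearance requirement that CR itself does not list. Because the other lists are introduced as complete, a site or a programmer applying them literally would credit remission to a patient with visible leukaemia in the blood.

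Several results use these categories. Objective 1.2.1 and the estimation paragraph of Section 9.1 use CR plus CRi. Objective 1.2.2 adds CRh and MLFS. The expansion cohort in Section 9.1 is judged on 13 or more responses among 30, so a total of 12 becomes a positive result with one extra counted responder. The Schema and Section 9.1 also use CR, CRi and CRh to mark the move from induction to maintenance.

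**Working it through.** **Step 1: apply the lists.** Take hypothetical patients with 3% marrow blasts, platelets 120,000/µL, no extramedullary disease, transfusion independence and blasts without Auer rods in the blood. Vary the neutrophil count and the blast history.

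| Patient | Neutrophils/µL | Blood blasts | CR | CRi | MLFS | CRh | Relapse (12.1.30) |
|---|---|---|---|---|---|---|---|
| A | 1,200 | cleared, then returned | yes | no | yes | no | yes |
| B | 600 | cleared, then returned | no | yes | yes | no | yes |
| C | 1,200 | never cleared | yes | no | yes | no | no |
| D | 600 | never cleared | no | yes | yes | no | no |

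B and D are the clearest cases. Their counts satisfy CRh (neutrophils above 500, platelets above 50,000), and they fail it only on the blood-blast line, yet they are CRi. Patients A and C would also meet CRc if an abnormal karyotype had reverted to normal. If the blasts carry Auer rods, CR, CRi and MLFS are all refused, so the gap concerns Auer-negative blasts.

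The relapse column depends on history, because 12.1.30 speaks of blasts reappearing. C and D do not meet it. A and B do, unless the last sentence of 12.1.31 governs every relapse.

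**Step 2: reproduce the design figures.** Inputs from Section 9.1: n = 30, success at 13 or more responses, null rate 0.30, target rate 0.50.

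- Type I error = Σ(x = 13 to 30) C(30,x) · 0.30^x · 0.70^(30−x) = 0.0845. The plan states 0.084.
- Power at 0.50 = 0.8192, so type II error = 1 − 0.8192 = 0.1808. The plan states 0.181.

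Both reproduce. The omission does not affect the sample-size calculation itself.

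**Step 3: illustrate the effect.** The documents do not say how often marrow blasts are below 5% while blasts circulate. Assume that the gap adds f to a true rate of 0.30, and recompute P(X ≥ 13) with n = 30 and p = 0.30 + f.

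| f (assumed) | Expected extra responders, 30 × f | P(13 or more of 30) |
|---|---|---|
| 0 | 0 | 0.084 |
| 0.01 | 0.3 | 0.105 |
| 0.02 | 0.6 | 0.129 |
| 0.033 (1/30) | 1.0 | 0.166 |

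One added percentage point is enough to pass the 0.10 target.

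**The case against.** The best defence is that the passages can be read together. Section 12.1 cites an outside criteria set and says blood is examined. If CRh meets every CR criterion except counts, absence of circulating blasts may already be implied for CR. On that reading this is a drafting omission. That is plausible, but the cited criteria cannot be checked from the documents, and the lists claim to be complete. Because CRh states the item expressly, its absence elsewhere can equally be read as intended.

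Other limits stand. Auer-rod blasts already bar the four categories. Section 9.1 frames the 13-of-30 test on the CR rate and uses CR/CRi only in the following paragraph. If the test uses CR alone, the CRi route cannot affect it, and a miscounted patient would also need full count recovery and transfusion independence.

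A reader might infer three stronger conclusions, which the documents do not support:

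- **Every such patient is in remission and relapse on the same day.** This needs blasts that cleared and returned, and a narrow reading of 12.1.31.
- **The resistant-disease category contradicts CR/CRi**, because it refers to patients "with evidence of persistent leukemia by blood and/or bone marrow examination". It applies only after failure to achieve CR, CRc, CRi or PR, so a patient already credited with CR or CRi is outside it.
- **PFS or remission duration would start from a relapsed state.** Remission duration is not an objective, and no section starts PFS at remission.

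**Conclusion.** The inconsistency is real and follows from the text alone. The four closed lists admit a patient with Auer-negative circulating blasts, and CRh does not. For the CR/CRi rate and the overall response rate, the possible error is in one direction: upward. For the 13-of-30 decision, it matters for patients who meet full CR, or for CRi patients if CRi is counted.

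The size is unknown. The range of 0.105 to 0.166 rests on an assumed 1 to 3.3 points added to a true 30% rate and is an illustration, not an estimate. A reader might infer that the stated error rates are wrong. They are not: they are correct for the rule, and the question is which patients enter the count. The definitions should be corrected because the misclassification is certain under a literal reading and the repair is small, although the frequency may be low.

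**What to change.** Reconcile the definitions in Section 12.1 so that all remission categories treat circulating blasts alike:

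1. Add absence of circulating leukaemic blasts on the peripheral blood differential to the endpoint definitions of CR, CRc, CRi and MLFS.
2. Do not copy the parenthesis in the CRh item on flow cytometry and Auer rods. Its meaning is unclear, and the biomarker plan in Section 5.6 lists immunophenotyping on marrow aspirate rather than blood.
3. State whether the last sentence of 12.1.31 applies to all relapse or only to cytogenetic relapse.

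The change concerns endpoint classification. Because the same categories mark the move to maintenance, the sponsor should check that the Schema and Section 9.1 remain consistent with the reconciled text.

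Cost: one line in each of four definitions and one clarification. Section 11 already schedules a blood count with differential twice weekly in induction, at the start of each maintenance cycle and at relapse or end of treatment. The sample size and the threshold of 13 do not change. The observed response rate may be slightly lower. If the 50% target was set with the looser definition in mind, which the documents do not say, a loss of 1 to 3.3 points would lower power from 0.819 to between 0.789 and 0.707.
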